2.4 Study Hypothesis

The NCPRR is descriptive in nature for the purpose of hypothesis generation. There is no specific hypothesis for each specific outcome of interest.

3. PATIENT REGISTRY STUDY PLAN

3.1 Registry Design

The NCPRR is established on the basis of the NHRS of 3 Nordic countries: Denmark, Sweden, and Norway.

The study period will be between 01 January 2009 (starting date) and 31 December 2019 (ending date). Interim study reports will be developed for yearly submission to the Agency. Each annual report will describe include events occurring from 01 January through 31 December of the reporting period with cumulative results. All data sources will use the same cutoff date in calendar time, December 31st of the latest year for all data obtained from the NHRS databases. The patient experience (patient time) for all patients who receive at least 1 dose of romiplostim therapy will be included in the romiplostim exposure cohort after they receive romiplostim. The patient experience with ITP time before romiplostim exposure will be included in the romiplostim unexposed cohort, along with that for all adult chronic ITP patients who never receive romiplostim therapy during the study period.

Adult chronic ITP cohorts (romiplostim Exposed Cohort and Unexposed Cohort) include adult patients who are identified as having chronic ITP (incident and prevalent cases through both hospital discharge registry and outpatient clinic registry, as described by [Frederiksen and Schmidt, 1999](#)) on or after the starting date, and up to 1 year prior to the ending date. All patients will be followed-up for **at least 1 year and up to 11 years** in either of 2 cohorts: the romiplostim Exposed Cohort or Unexposed Cohort. Incident and recurrent outcomes of interest will be assessed on an annual basis.

All clinical outcomes (eg, thrombotic/thromboembolic events, hematological malignancies, and other potential outcomes of interest) will be identified by International Classification of Diseases – 10th Revision (ICD-10) codes from the NHRS databases (eg, hospital discharge registry, outpatient clinic registry, pathology registry, death registry, cancer registry, birth registry, and prescription registry) or by review of electronic medical records and/or paper medical charts. As needed, suspected and identified cases will be medically confirmed by review of electronic medical records and/or paper medical charts, laboratory testing results, BM biopsy reports, pathology data, pharmacy data, and other relevant health records. Laboratory data will be used to determine thrombocytosis and worsened thrombocytopenia after cessation of romiplostim.

Because ITP is a diagnosis of exclusion and secondary causes of thrombocytopenia may be difficult to diagnose, some patients will require review of NHRS databases, medical records (electronic and/or paper charts), and laboratory data including bone marrow exams, if any, prior to their first diagnosis of ITP. These will include the relevant time periods prior to their first diagnosis of ITP for all patients who have a history of other primary thrombocytopenia (D69.4) or any condition from [Appendix 2](#) prior to the first diagnosis of ITP.

Cases with either increased BM reticulin or BM fibrosis (with/without associated clinical signs) and hematological malignancies (AML and MDS) will be ascertained using electronic medical record review. Confirmation of the diagnosis of BM reticulin/collagen fibrosis or AML/MDS will be accomplished by evaluation of the results of BM biopsies.

Selected data fields of each adult chronic ITP patient (prevalent cases as of 01 January 2009 and incident cases thereafter) and of patients who receive romiplostim therapy during the study period, will be extracted and analyzed to evaluate the endpoints listed in [Section 6.2](#). These selected data fields include those for the patient population using other thrombopoietic agents, since these agents could have a confounding impact on the occurrence of study outcomes such as BM fibrosis. In addition, the study will last up to 11 years and it will include both prevalent cases between 1996 and 2008 and incident cases from 2009 through 2018. The diagnoses, treatment procedures, medication, and practice patterns may be significantly changed; therefore, the study will use an inception cohort approach to define the study cohort based upon year of initial ITP diagnosis. Dependent upon sample size, the inception cohorts can be established as from 1996 to 2000, 2001 to 2005, 2006 to 2010, 2011 to 2015, and 2016 to 2018.

Patients and incidence rate of study outcomes will be compared among these inception cohorts.

To describe the romiplostim off-label utilization pattern, the study will also include patients without an adult chronic ITP diagnosis, but who are exposed to romiplostim. An example would be the inclusion of patients diagnosed with pediatric ITP, MDS, HIV/AIDS diagnoses, and who have received romiplostim therapy. Patients exposed to romiplostim with off-label use will be directly identified by drug codes for romiplostim as the codes are adopted in each participating country.

These selected NHRS databases have been previously used to determine the safety profile of pharmaceuticals, and have been considered one of best PV and epidemiology tools by regulatory authorities, epidemiologists, and safety specialists in both the clinical medicine and research communities ([Frank, 2000](#)).

Prospective annual analysis will be conducted for the study, and all proposed research outcomes will be assessed in these annual analyses. The annual assessment will be descriptive in nature due to the small sample size and uncertainty of the diagnosis of some outcomes in each assessment. Results from these annual assessments will be submitted to the regulatory agency in appropriate context through the romiplostim Periodic Safety Update Report (PSUR). In the case a significant risk is observed in an annual assessment, an urgent ad hoc report will be communicated to the regulatory agency in the defined time frame according to Amgen Standard Operating Procedures (SOPs).

The registry also can serve as an infrastructure to assess any other newly detected safety signals during post marketing. However, new research outcomes must be reviewed and approved by the NCPRR Scientific Committee before they may be added to the study. Such modification of the study protocol will be communicated to the regulatory agency.

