Cases with either increased BM reticulin or BM fibrosis (with/without associated clinical signs) and cases of hematological malignancies or disorders (eg, AML and MDS) will be ascertained using electronic medical record review. Confirmation of the diagnosis of reticulin/collagen BM, reticulin/collagen fibrosis or hematological malignancies and disorders will be carried out by evaluation of the results of BM biopsies.

The 3 selected Nordic countries gather all health-related data on their citizens through a complex system of interlinked databases. The Danish government, for example, has compiled nearly 200 registry databases (some initiated in the 1930s) on everything from medical records, hospitalization, prescriptions, laboratory and pathology results, a cancer registry, and death certificates to socioeconomic data regarding jobs and salaries. What makes the databases a prime research tool is the fact that they are all linked by the 10-digit personal identification

number, called CPR, that follows each Danish citizen from birth to death. The NHRS and related databases in Norway and Sweden are similar to Danish system.

Selected data fields for each adult chronic ITP patient (prevalent cases as of 01 January 2009, and incident cases thereafter), and patients who receive romiplostim therapy during the study period, will be extracted and analyzed to evaluate the endpoints listed in [Section 6.2](#). These selected data fields include those for the patient population using other thrombopoietic agents, since these agents could have a confounding impact on the occurrence of study outcomes such as BM fibrosis. In addition, the study will last up to 11 years, and will include both prevalent cases between 1996 and 2008 and incident cases from 2009 to 2018. The diagnoses, treatment procedures, medications, and practice patterns may be significantly changed; therefore, the study will use an inception cohort approach to define the study cohort based upon year of initial ITP diagnosis. Depending upon the sample size, the inception cohorts may be established for the following periods: 1996 to 2000, 2001 to 2005, 2006 to 2010, 2011 to 2015, and 2016 to 2018. Patients and incident rate study outcomes will be compared among these inception cohorts.

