4.1 Sub-Patient Group Identification

The adult chronic ITP study population is identified using diagnostic codes (ICD-10: D69.3-D69.4) for at least 6 months after the first primary ITP diagnosis, and as having received at least 1 ITP medication, and/or had a splenectomy procedure during this 6-month time period. Electronic medical records will be reviewed to confirm the diagnosis. Confirmation of the diagnosis of ITP will be carried out by clinical presentations and/or related treatment. Based upon the status of romiplostim therapy, these patients will be segregated into the Exposed Cohort and the Unexposed Cohort. The index date for patients in romiplostim Exposed Cohort is defined as the first date of receiving romiplostim therapy.

The Index Date in the exposed cohort will be the date of first exposure to romiplostim. A patient who has not been exposed to romiplostim will have an Index Date imputed based upon the date of diagnosis using 2 methods: 1) if the date of diagnosis is prior to 01 April 2009, the Index Date will be imputed as 01 April 2009 (the first date of romiplostim availability), and 2) if the date of diagnosis is 01 April 2009 or later, the date of diagnosis will be imputed as the Index Date.

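### Outcome rates are to be compared among diagnosis-year cohorts followed only from 2009, so distant cohorts share almost no disease duration and their crude rates cannot separate diagnosis era from disease stage and survival

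*Protocol*

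**What the plan says.** Section 3.1 gives the reason for the grouping and the grouping itself: "The diagnoses, treatment procedures, medication, and practice patterns may be significantly changed; therefore, the study will use an inception cohort approach". The bands follow: "the inception cohorts can be established as from 1996 to 2000, 2001 to 2005, 2006 to 2010, 2011 to 2015, and 2016 to 2018". Forming them depends on sample size. The comparison is then stated without further condition: "Patients and incidence rate of study outcomes will be compared among these inception cohorts". The synopsis says the same: "Patients and incident rate study outcomes will be compared among these inception cohorts".

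The same section sets the study period at 01 January 2009 to 31 December 2019 and describes the patients who enter as "prevalent cases as of 01 January 2009 and incident cases thereafter". For unexposed patients, section 4.1 fixes the start: "if the date of diagnosis is prior to 01 April 2009, the Index Date will be imputed as 01 April 2009". For exposed patients the Index Date is the first romiplostim dose. Section 7.3 counts time at risk from first exposure or from the Index Date, not from diagnosis.

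Disease duration appears elsewhere. Section 12.7 lists it as a stratifier to be used as needed (under 1 year, 1 to 3 years, 4 years or more). Section 12.3 allows it as an extra regression covariate.

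**The concern.** An inception cohort is followed from the start of disease. The pre-2009 groups are not. A patient diagnosed in 1996 contributes follow-up only if alive, resident and still identified as a chronic case some 13 years later. A patient diagnosed in 2017 is seen only in the first few years.

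Bleeding, thrombosis, haematological malignancy emerging after an ITP diagnosis, and marrow findings may all vary with years since diagnosis and with selection by survival. If they do, the early and late groups will show different rates even when practice had no effect at all. Sections 3.1 and 12.8 intend the results for annual regulatory reporting and signal generation, where such a difference could be attributed to the wrong cause.

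**Working it through.** **The plan's own figures.** The protocol gives no figure for this comparison, but section 3.5 supplies the patient flow.
- Prevalent: 570 × 13 = 7410; × 0.20 = 1482; × 0.95 = 1408; × 0.25 = 352 exposed.
- Incident: 5700 × 0.20 = 1140; × 0.95 = 1083; × 0.25 = 271 exposed.
- Exposed total: 352 + 271 = 623, as stated. The rest is 1408 + 1083 − 623 = 1868, against 1860 stated (0.4% apart).
- Chronic patients per diagnosis year: 570 × 0.20 × 0.95 = 108.3.

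**Observable disease duration.** Shortest = max(2009.0 − diagnosis date, 0.5), the 0.5 being the chronic-ITP requirement of more than 6 months. Longest = 2020.0 − diagnosis date.

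| Diagnosis years | Years since diagnosis observed | Mean |
|---|---|---|
| 1996-2000 | 8.0 to 24.0 | 16.0 |
| 2001-2005 | 3.0 to 19.0 | 11.0 |
| 2006-2010 | 0.5 to 14.0 | 6.4 |
| 2011-2015 | 0.5 to 9.0 | 3.7 |
| 2016-2018 | 0.5 to 4.0 | 1.7 |

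The ranges follow from the stated dates; the means assume uniform diagnosis dates and no losses. Taking section 4.1 literally (start 01 April 2009, or at diagnosis if later), the lower limits become 8.25, 3.25, 0, 0 and 0.

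**Overlap of person-time.** Let f(t) be the share of a cohort's person-time at t years since diagnosis. Overlap = ∫ min(f₁, f₂) dt.
- 1996-2000 v 2016-2018: no common t, so 0.
- 1996-2000 v 2011-2015: only 8 to 9 years is shared. There f₁ = (t − 8)/55 and f₂ = (9 − t)/30. They cross at t = 8 + 55/85 = 8.647, height 0.01176; overlap = ½ × 1 × 0.01176 = 0.006.
- 2001-2005 v 2016-2018: 0.008.
- Two bands apart: 1996-2000 v 2006-2010, 0.17; 2001-2005 v 2011-2015, 0.21; 2006-2010 v 2016-2018, 0.25.
- Adjacent: 1996-2000 v 2001-2005 are equal trapezoids shifted by 5 years, giving 6/11 = 0.545. 2011-2015 v 2016-2018: 2.5/6 + 0.5/6 = 0.50. The highest is 2006-2010 v 2011-2015, 0.62.

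**Usable person-time, 1996-2000 v 2011-2015.** In the shared year each cohort has ½ × 108.3 = 54 patient-years. Totals are 541.5 × 11 = 5957 and 541.5 × 6.0 = 3249, so 54 is 0.9% and 1.7%. With a start at 01 April 2009 it is ½ × 0.75² × 108.3 = 30.5; with 3% yearly attrition as well, about 30.5 × 0.97^8.75 = 23.

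**Do the section 12.7 strata repair it?** The 4+ band holds 100% of 1996-2000 time (mean 16.0 years), 541.5 × 2.5 / 3249 = 42% of 2011-2015 time (mean 5.7 years) and 0% of 2016-2018 time. Within it the first group is still about 10 years further from diagnosis than the fourth.

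**Illustration with no era or practice effect (assumed hazards).** If the hazard halves after 4 years, the 2016-2018 v 1996-2000 rate ratio is 1/0.5 = 2.0. If it doubles after 8 years, it is 1/2 = 0.50. For the adjacent pair 2006-2010 v 2001-2005, with 27.7% and 0.9% of time before year 4, halving gives (0.277 + 0.723 × 0.5)/(0.009 + 0.991 × 0.5) = 0.6385/0.5045 = 1.27: smaller, and removable by aligning on duration.

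**The case against.** The strongest reply is that little rests on this comparison. The study is descriptive and has no hypotheses (section 2.4), comparative analyses are exploratory (section 12.4), forming the cohorts depends on sample size, and the primary objective (section 1.1) is an incidence rate in romiplostim recipients. All of that stands and limits the weight of the point.

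A second reply is that the tools for a sound analysis are already listed. Disease duration is a stratifier, a propensity variable and a covariate, and stratification by spans of years tied to changing practice is allowed in sections 12.3, 12.4 and 12.7. Time scale and band limits could be left to a statistical analysis plan. This stands in part. But the protocol itself fixes the grouping, its rationale and the rate comparison. Duration adjustment is optional, the top band is open, and no later plan can align durations that are never observed; for those pairs a covariate only extrapolates.

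A reader might infer more than the text supports:
- That the whole cohort comparison shows disease stage rather than practice and cannot serve its purpose. Adjacent cohorts overlap by 50 to 62%, so an aligned comparison is feasible there.
- That practice in 1996-2008 is never seen. Outcome follow-up starts in 2009, but prior ITP medication and splenectomy are propensity variables (section 12.3), and section 2.3 describes lifetime information for exposed patients.
- That rate differences will be reported as practice effects. No sentence says so.
- That section 12.2 has the same defect. It tabulates characteristics and compares utilization among inception cohorts, not outcome rates.

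**Conclusion.** The point holds for crude outcome-rate comparisons between distant diagnosis-year cohorts, as stated in the synopsis and section 3.1. Those contrasts cannot separate diagnosis era from disease duration and survival to 2009. Overlap is nil for the first and last cohorts and under 1% for the next most distant pairs.

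The duration ranges need only the protocol's dates. The overlap and person-time shares also assume uniform diagnosis dates, a constant 108.3 chronic patients per diagnosis year and no later losses. They should be read as shares, not forecasts of person-years. The reading also takes sections 4.1 and 7.3 as governing the start of time at risk. Section 3.1 puts ITP time before romiplostim into the unexposed cohort; if that were taken to include time before 2009, only patients who survived to be treated would supply it, which adds survivor bias.

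This should be corrected, but it does not threaten the primary result.

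**What to change.** In the synopsis and section 3.1:
- Reserve the term inception cohort for patients diagnosed from 2009 on. Call the 1996-2008 patients prevalent cases, and report prevalent (1996-2008) and incident (2009-2018) patients separately. The 2006-2010 band mixes both and should be split at the end of 2008.
- Replace the unconditional rate comparison with one made only within shared bands of time since ITP diagnosis, with delayed entry at the Index Date. State that no rate contrast is made for pairs without overlap.

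In section 12.7, split the 4+ band, for example into 4 to 7, 8 to 12 and 13 or more years. To describe practice change, use the calendar-span stratification already allowed in sections 12.3, 12.4 and 12.7, within duration bands. Section 12.2 needs no change on this point beyond the cohort names.

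The cost is wording and a re-tabulation of the same person-time; no new data are needed. The downside is sparser strata with few events, and the loss of rate contrasts between the most distant cohorts.

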3.2 Number of Physicians

The NCPRR is established on the basis of the NHRS databases of Denmark, Sweden, and Norway. The number of physicians is unknown, but all physicians who prescribe romiplostim in Denmark, Sweden, and Norway will be included in the study.

3.3 Study Setting and Source Population

The NCPRR is a prospective annual assessment of study outcomes established on the basis of the NHRS. The study population includes chronic ITP patients, defined as

patients who have been diagnosed with ITP for more than 6 months, and who continually receive ITP treatment (eg, ITP medication) and/or have had a splenectomy procedure. All qualified adult chronic ITP patients will be the source population, regardless of romiplostim therapy status.

To describe the romiplostim off-label utilization pattern, the study will also include patients without an adult chronic ITP diagnosis who are exposed to romiplostim.

3.4 Selection of Participants (or Subject Eligibility)

3.4.1 Inclusion Criteria

Subjects in the NCPRR will be those whose health information is recorded by the NHRS of Denmark, Norway, or Sweden.

The eligible adult cITP romiplostim-exposed patients for the NCPRR must meet all of the following criteria:

- Patients must be 18 years or older at the time of chronic ITP diagnosis,
- Patients will have romiplostim therapy between 01 January 2009 and 31 December 2018, and
- Patients will have at least 6 months of medical information prior to initial date of receiving romiplostim treatment (Index Date), data from which will establish a baseline of study subjects.

The eligible adult cITP romiplostim-unexposed patients for the NCPRR must meet all following criteria:

- Patients must be 18 years or older at the time of chronic ITP diagnosis,
- Patients will not have received romiplostim therapy prior to or during the study period between 01 January 2009 and 31 December 2019, and
- Patients will have at least 6 months of medical information in the study period. The data from this period will establish baseline of subjects in the comparison group.

Eligible romiplostim-unexposed cITP patients will be the source of comparison cohorts for romiplostim-exposed cITP patients. Because potential confounding factors (eg, severity of ITP condition) may cause some biases for the study, however, robust propensity scoring and adjusted analyses will be essential ([Section 12](#)). In addition, appropriate contextualization from other recognized data sources will be used in comparisons to address selection biases.

In addition, according to initial dates of receiving romiplostim therapy among patients in the Exposed Cohort, the follow-up time period will be separated into 2 periods: (1) follow-up time period prior to romiplostim exposure, and (2) follow-up time period following romiplostim exposure. Patient experiences in the follow-up time period prior to the initial date of receiving romiplostim therapy will be considered as another “within-patient” comparison with the patient experiences during the follow-up time period after the initial date of receiving romiplostim therapy.

Eligible romiplostim Off-Label-Exposed patients will be any patient who received romiplostim therapy without an adult chronic ITP diagnosis.

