Patient records will provide person-years of data for each study cohort (Exposed and Unexposed). The incidence rates will be assessed for both the exposure and non-exposure cohorts. The incidence rates will also be assessed for both the follow-up time periods prior to and after the initial date of receiving romiplostim in the Exposed Cohort.

When sample size permits, Kaplan-Meier survival curves will be constructed for patients with events of interest for the Exposed Cohort and Unexposed Cohort.

Due to the intrinsic limitations of this type of observational study, the effects of confounding by indication may bias the results when the incidence rates of study outcomes are compared between the Exposed Cohort and Unexposed Cohort. The effects associated with confounding by indication will be considered in all analyses in order to reduce the possible impact of these effects in the comparison.

In order to reduce the effects of confounding by indication, a propensity score will be developed for each adult chronic ITP patient. A stratified analysis (by propensity score strata, disease severity, and platelet count) and multiple regression analyses will be carried out. As needed, the age-, sex-, and propensity score-matched approach may be also applied to the adult chronic ITP study population. (Inherent limitations related to propensity score are addressed in [Section 8](#)).

Cox regression models using romiplostim exposure as a time-varying covariate may be used to compare the event rates among ITP patients and the reference cohort, with an estimation of the hazard ratio and associated 2-sided 95% confidence interval. Other treatment exposures, health status, and disease condition may also be considered for inclusion in the model as time-varying covariates. The analysis will adjust for potential confounders and propensity score. Multiple event models such as Andersen-Gill models may be used to evaluate recurrent events if applicable. However, this analysis is only intended to serve exploratory and hypothesis generation purposes.

Means and 95% confidence intervals of laboratory numerical outcomes (eg, platelet counts) will be obtained and compared between the associated cohorts, and among different predefined time periods related to romiplostim treatment ([Section 7.1](#)).

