- A hypothetical concern regarding hematopoietic growth factors is that they may enhance the growth of existing malignancies or promote the growth of new malignancies that are influenced by the receptor-ligand axis. The TPO receptor is predominantly expressed on cells of the myeloid lineage, and there is no confirmed expression on solid tumors ([Graf et al, 1996](#); [Columbyova et al 1995](#)); therefore, it is not expected that romiplostim will promote the growth of solid tumors. In the ITP clinical program, there is no evidence of increased neoplasia, including hematopoietic malignancies; there is, however, a potential risk that TPO receptor agonists may stimulate the progression of existing hematopoietic malignancies or MDS among patients with thrombocytopenia caused by conditions other than ITP. Ongoing clinical studies in other patient populations, including MDS, will help to assess this potential risk.

Other potential risks include:

- Thrombotic/thromboembolic complications
- Progression of increased reticulin to an irreversible BM fibrotic state

In Europe, the product label includes further dose adjustment rules that have been specified by the European regulator as a risk minimization measure of thromboembolic risk and have not been tested in clinical trials.

Dose adjustment rules as specified in the European label

Platelet count (x 10 ⁹ /L)	Action
<50	Increase once weekly dose by 1 mcg/kg
>150 for 2 consecutive weeks ^a	Decrease once weekly dose by 1 mcg/kg
>250 ^a	Do not administer, continue to assess platelet count weekly After the platelet count has fallen to < 150 x 10 ⁹ /L, resume dosing with once weekly dose reduced by 1 µg/kg

^a Due to the inter-individual variable platelet response, in some patients platelet count may abruptly fall below 50 x 10⁹/L after dose reduction or treatment discontinuation. In these cases, if clinically appropriate, higher cut-off levels of platelet count for dose reduction (200 x 10⁹/L) and treatment interruption (400 x 10⁹/L) may be considered according to medical judgment

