3.4.2 Exclusion Criteria

Patients who are enrolled in a clinical trial for other TPO receptor agonists (eg, clinical trials for eltrombopag) will be excluded from the study.

Patients are excluded from the cohorts of chronic ITP patients if either of the following is present:

1. Any diagnosis of another condition associated with thrombocytopenia other than chronic ITP listed in [Appendix 2](#) at any time prior to or within 6 months after the qualifying diagnosis for chronic ITP. Examples of thrombocytopenia associated with other diseases and conditions include systemic lupus erythematosus (SLE), HIV infection, hepatitis C virus infection, malignancy, lymphoproliferative disorders, and myelodysplastic syndrome.
2. Lack of a platelet count below $150 \times 10^9/L$ without obvious cause in the 6 months before or after their first ITP diagnosis code

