8. POTENTIAL SOURCES OF BIAS IN STUDY DESIGN

There are 4 key potential sources of bias in the study design:

Disease severity: Since romiplostim is more efficacious in treating chronic ITP than currently-marketed products, patients with more severe conditions and longer durations of the disease will receive the treatment, which should be considered as a confounding factor. Such a factor may cause a bias in the evaluation of long-term safety of romiplostim. Patients with a more severe ITP condition, for example, are more likely to have clinically significant bleeding events. Without effective methods to reduce the bias effect, the study results are questionable. To address the issue, propensity scores may be used to create strata in which the patients who are exposed and unexposed are alike

in variables that may affect outcome by forming comparisons between patients at the time of introduction to romiplostim. These variables may include disease severity, duration of disease, prior medications, and other collected variables that influence outcome. However, the prescribing patterns may not be homogeneous across the population, thereby causing minimal overlap in attributes between the exposed and unexposed. Additionally, there may be unobserved (unmeasured) differences that are not represented by the collected data. This could negatively impact the utility of propensity score stratification as there would be fewer unexposed patients with similar characteristics to the exposed patients to select for comparison.

Inconsistent reading of BM biopsy results: Because BM biopsies are taken at different time periods and reviewed by different pathologists, the consistency may be questionable, and may cause some bias. To address this issue, all BM specimens for adult chronic ITP patients will be requested to be stained for reticulin and collagen. In addition, to ensure these standards, 2 pathologists will independently, and in a blinded fashion, review all BM biopsy specimens. If diagnostic conclusions from both pathologists are inconsistent, a third pathologist will re-review the biopsies again to ascertain a final diagnosis.

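### The within-patient before/after rates use pre-start time that requires survival to romiplostim, so they can be biased upward for fatal outcomes, AML/MDS and primary myelofibrosis

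*Protocol*

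**What the plan says.** Section 3.4.1, and the Synopsis under Comparison Group, divide Exposed Cohort follow-up at the first romiplostim dose. On the earlier part: "Patient experiences in the follow-up time period prior to the initial date of receiving romiplostim therapy will be considered as another" comparison, labelled within-patient. The Synopsis, Statistical Considerations, adds for Exposed Cohort patients: "The incidence rates will also be assessed for both the follow-up time periods prior to and after the initial date of receiving romiplostim". Section 12.2 describes outcomes in the periods before and after exposure. None of these places exempts an outcome.

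Other rules that bear on the earlier segment:

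- Section 3.4.1 requires of exposed patients: "Patients will have at least 6 months of medical information prior to initial date of receiving romiplostim treatment".
- Section 3.4.2 with Appendix 2 excludes patients with hematological malignancy, MDS or myelofibrosis "at any time prior to or within 6 months after the qualifying diagnosis for chronic ITP".
- Section 7.3 starts time at risk at first exposure, so it defines no denominator for the time before.
- Section 8 says of romiplostim that "patients with more severe conditions and longer durations of the disease will receive the treatment", and that "Patients with a more severe ITP condition, for example, are more likely to have clinically significant bleeding events". Its four bias sources are disease severity, biopsy reading, case ascertainment and missing values.
- Section 3.1 also counts pre-romiplostim time as unexposed time, together with that of never-exposed patients. The Synopsis and Section 12.4 offer a Cox model with time-varying exposure, as an option.

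**The concern.** A patient contributes before-time to this contrast only because of something that happens later: the first dose. Anyone who dies first never joins the Exposed Cohort, and their event and person-time drop out of the before segment. The same holds for any event that in practice stops a start. The after segment carries no such condition. Each patient's before-time is selected on the absence of the event, so covariate adjustment cannot restore what is missing.

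For bleeding the selection can run the other way. If a recent bleed is what prompts treatment, the months before the Index Date are a bad spell by selection, and the rate falls afterwards by regression to the mean.

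The stakes are in signal detection. The annual assessments go to the regulator, and an apparent significant risk leads to an ad hoc report (Section 3.1). In the Synopsis the within-patient contrast comes straight after the warning about confounding by indication, so it may be taken as the cleaner comparison. For fatal and malignant outcomes it is not.

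**Working it through.** **1. The plan's own figure.** No figure is stated for this contrast, only the size of the cohort behind it (Section 3.5). Prevalent: 570 × 13 = 7,410; × 0.20 = 1,482; × 0.95 = 1,408; × 0.25 = 352. Incident: 5,700 × 0.20 × 0.95 × 0.25 = 271. Total 352 + 271 = 623, as stated.

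**2. What can appear before the first dose.**

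- Fatal events: none, by construction.
- Hematological malignancy, MDS, myelofibrosis: none up to 6 months after the qualifying diagnosis, by rule. After that, a non-fatal case can occur and be counted if the patient still starts.
- Other non-fatal events: counted, unless they keep the patient from starting.

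**3. Upward bias with no drug effect.** Let λ be the event rate and f the share of events that are fatal or prevent a start. The after rate is λ. The before rate among later users is about λ(1-f). The ratio is 1/(1-f).

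| f (assumed) | 1/(1-f) |
|---|---|
| 0 | 1.00 |
| 0.25 | 1.33 |
| 0.50 | 2.00 |
| 0.75 | 4.00 |
| 1 | unbounded |

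This was checked by simulation with a true rate ratio of 1, λ of 0.2% and 0.5% per year, a 5% per year chance of starting, and 11 years (rates and start chance are assumptions). The after/before ratio was 1.0 at f = 0, about 1.4 at 0.3, 2.0 to 2.1 at 0.5 and 4.3 to 4.7 at 0.8. At 0.8 the formula gives 5, and numerical integration of the same model gives 4.93 to 4.97; the gap is simulation noise from few before-events. With all not-yet-exposed chronic ITP time as comparator, including patients who die or never start, the ratio returned to 0.97 to 1.03.

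**4. Possible downward bias for bleeding.** Let b be the bleeding rate, r the share of bleeds that prompt a start, and s = 0.05 per year the rate of starting for other reasons (all assumed). The share of starts prompted by a bleed is P = br/(br + s). The before rate is b(1-r) + P/E, with E the mean length of before-time.

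Example, b = 0.05 and r = 0.1: P = 0.005/0.055 = 0.091. In the 6-month window of Section 7.1, 0.045 + 0.091/0.5 = 0.227, so the ratio is 0.05/0.227 = 0.22. Over all pre-start time E is about 4.95 years: 0.045 + 0.091/4.95 = 0.063, ratio 0.79.

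| r | All pre-start time | 6-month window |
|---|---|---|
| 0 | 1.0 | 1.0 |
| 0.1 | 0.79 to 0.84 | 0.22 to 0.26 |
| 0.3 | 0.61 to 0.76 | 0.10 to 0.16 |

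The ranges cover b from 0.05 to 0.2. Pooled not-yet-exposed time gave 0.98 to 1.01.

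**5. Counts.** A 6-month window for 623 patients is 623 × 0.5 = 311.5 patient-years. At an assumed 0.1% to 0.5% per year, that is 0.3 to 1.6 expected events, against 4,234 × 0.001 to 0.005 = 4.2 to 21.2 after the start. Even without bias, the chance of no before-event is exp(-0.31) = 73% down to exp(-1.56) = 21%.

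**The case against.** The strongest reply is that the protocol never presents this contrast as confirmatory. Every comparison is labelled exploratory, no hypothesis is stated, and signals are to be read with caution against internal and external data. Section 12.4 says AML and MDS are too few for meaningful comparison and turns to case descriptions. Section 12.6 does likewise for marrow outcomes unless numbers suffice. The within-patient contrast supplements the pooled analysis, and it removes fixed differences between patients, which the protocol admits may be large and partly unmeasured. Section 13 does mention unmeasured selection through prescribing behavior.

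Much of this stands and limits the consequence. It does not remove the bias: rates are still to be calculated before and after, and the reason given for the exploratory label is confounding between exposed and unexposed patients, not selection within users.

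Stronger readings that a reader might infer are not supported:

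- That any malignancy, marrow finding or thrombosis rules out a later start. Section 2.3 says that "TPO receptor agonists may stimulate the progression of existing hematopoietic malignancies or MDS", but of patients whose thrombocytopenia has causes other than ITP. No section bars a start.
- That pre-start time is certainly enriched for bleeding. Section 8 compares exposed with unexposed patients, and stable severity cancels within a patient. Section 12.3 lists bleeding history as a candidate predictor of treatment, which makes bleed-prompted starts plausible only.
- That the bias can be set against the relative risks of 2 to 4 in Section 11. That power statement concerns exposed versus unexposed patients.
- That an empty before-period would demonstrate the bias. Step 5 shows it is likely by chance.
- That the contrast should go for thromboembolism and marrow fibrosis too. Thromboembolism can be non-fatal and recur, and Sections 5.3 and 12.6 use before-and-after marrow data on purpose.

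**Conclusion.** The point holds as a structural bias of unknown size. For fatal events the before-count is zero by construction, so the after/before ratio says nothing about the drug. For AML/MDS and primary myelofibrosis the ratio can be biased upward by about 1/(1-f), that is 1.3 to 4 for an assumed f of 0.25 to 0.75; with f = 0 there is none. The exclusion rule up to 6 months after the qualifying diagnosis adds event-free time, which is mostly before the start. For bleeding and rescue treatment a downward bias is conditional on recent bleeding prompting the start, which the protocol does not state. The values of f, r and the background rates are assumptions. The exploratory status keeps the harm to misleading annual descriptions and signals, but the protocol should still be corrected, since it already contains the better comparator.

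**What to change.** In the Synopsis (Comparison Group and Statistical Considerations) and in Sections 3.4.1 and 12.2:

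- Do not use the within-patient before/after rate comparison for AML/MDS, primary myelofibrosis and fatal events. For these, use pre-start time only pooled with all other unexposed chronic ITP time, as Section 3.1 already provides, with exposure time-varying as in the Synopsis and Section 12.4.
- Keep the contrast for platelet counts, bleeding, ITP treatment, non-fatal thromboembolism and paired marrow data.
- For bleeding and ITP treatment, add a sensitivity analysis that leaves out a fixed window before the Index Date, for example 30, 60 and 90 days.
- In Section 8, name selection on survival to treatment and regression to the mean.

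Pooling does not by itself deal with the 6 months cleared by the exclusion rule if they count as unexposed time; the text should say whether they do.

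The cost is protocol wording, the loss of one descriptive contrast for rare outcomes, and less pre-index time in the sensitivity analysis: 30 to 90 days is about a sixth to a half of the 6-month pre-treatment period in Section 7.1.
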